### Significance

We created a unique partnership between a community-based non-profit organization (the MHCI) and a world-renowned academic research institute (Pennington Biomedical) to examine the effects of a health policy change in childcare centers on children's health behaviors. The **timing is ideal** to establish baseline values of the physical activity environment and behaviors of children, then to evaluate these environments and behaviors one year after the childcare centers receive training, programmatic support, and mandated regulations to achieve the new physical activity and screen-time regulations. Community stakeholders in the MHCI have identified childhood obesity prevention as a top priority, but the majority of parents fail to recognize obesity in preschool children, and many mistakenly think that obesity is not a health problem at this age. We seek a shift in the climate of the community to recognize that preschool is a critical opportunity to improve health behaviors in order to put children on a trajectory towards life-long healthy living.

### **Inclusion and Exclusion Criteria**

From the 10 selected childcare centers, 266 children and their parent(s) will be recruited to complete additional measures of physical activity and screen-time behaviors.

#### Inclusion Criteria:

- A child who is 3 or 4 years old
- Child spends at least 6 hours per day, 5 days per week at a participating childcare center
- Child will continue to attend the same childcare center for the next year

#### Exclusion Criteria:

- Parent/legal guardian is unwilling to provide written informed consent

### **Number of Subjects and Subject Timeline**

We plan to enroll 266 children. Each child will participate in the study for approximately 1 year. Surveys, anthropometric measures, fundamental motor skill assessments, and screen-time observations will take approximately 2 days to complete, and the child will be given an accelerometer to wear at home for 7 days at both baseline and 1 year follow-up. Staff members will spend approximately 2 weeks at each childcare center at baseline and 1 year follow-up to complete study procedures with each child.

### Study Timeline

This study will last from March 2016 until June 2018. A proposed timeline of all study procedures is listed below:

	March to April 2016	May 2016 to April 2017	May 2017 to April 2018	May to June 2018
MOP development and IRB submission	X			
Recruitment of children		X		
Baseline data collection		X		
1 year follow-up data collection			X	
Data management and analysis		X	X	
Manuscript preparation				X

### Recruitment Methods

All parents of children between the ages of 3-4 years at selected childcare centers will receive an informational handout/flyer and consent form to participate in **Aim 2** study procedures. Informational materials about the study may also be distributed to parents via email, mail, fax, phone, in-person, or through the school. Children for whom a completed consent form is returned by their parent or legal guardian will be eligible to complete additional measures of physical activity and screen-time behaviors. Out of the pool of 192 DOE licensed childcare centers, totaling a capacity for approximately 16,500 students, in EBR Parish, we do not envision difficulties enrolling 266 children for study participation. We aim to recruit all 266 children between May 2016 and April 2017.

### Train Schedule

Below are the procedures that will be completed during study participation.

	Baseline 1	Baseline 2	Follow-up 1	Follow-up 2
Consent	X			
Parent Survey	X		X	
Height	X		X	
Weight	X		X	
BMIz score	X		X	
TGMD-3		X		X
MABC-2		X		X
Accelerometry Application	X		X	
Accelerometry Return		X		X

### Procedures

**Consent Process.** Informed consent for the child will be obtained from one of the participant's parents/legally authorized representatives prior to conducting any study procedures. The parent/legally authorized representative will be given an informed consent form to read and sign indicating their permission to allow their child to participate in the study. Parents will return this consent form to the study staff before the

child's first visit. Because there is not a greater than minimal risk, informed consent will be obtained from one parent even if the other parent is alive, known, competent, reasonably available, and shares legal responsibility for the care and custody of the child.

Children will not be asked to provide documented assent due to their young age, but all procedures will be explained in child-friendly terms and a child's refusal to participate will be respected by study staff. However, if a childcare site has specific assent requirements, we will comply by creating a site-specific parental consent that includes the necessary language.

Parent survey. Parents will be asked to complete a questionnaire that will provide information on the child's sociodemographic characteristics, including sex, date of birth, and parents' marital status, highest level of education, family income, occupation, and employment status. The poverty guidelines developed by the Department of Health and Human Services will be used as our measure of socioeconomic status.

Anthropometric measurements. Height and weight of each child will be measured in a private setting with children dressed in light clothing. Height will be measured to the nearest 1.0 cm using a portable stadiometer. Weight will be measured to the nearest 0.1 kg using high-precision electronic scale. Body mass index (BMI) z-score will be calculated based on the child's age, sex, height, and weight, then compared to the 2000 Centers for Disease Control and Prevention (CDC) Growth Charts.

Fundamental Motor Skill Assessments. The Test of Gross Motor Development - 3rd edition (TGMD-3) and the Movement Assessment Battery for Children - 2nd edition (MABC-2) will be administered with the cooperation and support of the childcare center staff in small group settings. Groups of approximately 3-4 students will complete the assessments together. The TGMD-2 uses direct observation to evaluate performance on 13 skills including running, horizontal jumping, hopping, skipping, sliding, galloping, and balls skills (two-hand striking, one-hand striking, catching, kicking, overhand throwing, underhand throwing and dribbling). The TGMD-2 involves a trained administrator demonstrating the proper execution of the skill, and the participant is allowed one practice trial then two formal trials that will be evaluated. The MABC-2 examines eight tasks that are categorized as manual dexterity, balance, aiming and catching. This is a field-based assessment that examines correct performances on a variety of skills that are not evaluated by the TGMD-3 and will provide a holistic picture of children's motor abilities. These assessments will be audio and video recorded.

Physical activity. Physical activity and time spent in moderate to vigorous physical activity will be measured by a triaxial accelerometer (Actigraph GT3X+, Actigraph of Ft. Walton Beach, FL). Children will be measured on 7 full days during the baseline and follow-up periods. The child will be outfitted with the accelerometer on an elasticized belt, on the right mid-axillary line. The Actigraph is one of the most common accelerometers used for scientific purposes, and the GT3X+ version provides extensive data on steps/day and time spent in various activity intensities. Parents will be encouraged to have their child wear the accelerometer 24 hours per day for at least 7 days (plus an initial familiarization day and the morning of the final day), including 2 weekend days. During wear weeks, study staff will check accelerometry wear during school hours to assess for compliance. Accelerometer use will be documented and parents of children who do not have accelerometers on wear check days will be contacted via call, text, flyer, email, etc. as a reminder. The minimal amount of accelerometer data that will be considered acceptable is 4 days with at least 10 hours of

wear time per day, including at least one weekend day. Following the final day of data collection, the research team will verify the data for completeness using the most recent version of the ActiLife software (version 5.6 or higher; ActiGraph, Pensacola, FL) available at the time. The research team will ask the parents to have the children wear the accelerometer for additional days (to a maximum of 14 days) to ensure that minimal data requirements are met. Cut points will be assigned based on Van Cauwenberghe et al., with 0 to 372 counts per minute (CPM) classified as sedentary, 373 to 584 CPM as light, 585 to 880 CPM as moderate, and  $\geq 881$  CPM as vigorous. MVPA will be defined as total minutes  $\geq 585$  CPM.

**Screen time.** Screen time will be assessed using classroom observation at the childcare center (from the EPAO observation in Aim 1) and parent-report for screen-time outside of the childcare center. Parents will complete a survey adapted from Jago et al. to provide information about the child's screen-time (separately for TV, computer, games console and smartphone) on weekdays and weekend days. For each item the parent will be asked to report the time the child spent using it for (a) a normal weekday and (b) a normal weekend day, with response options: none; 1 to 30 minutes; 31 minutes to 1 hour; 1 to 2 hours; 2 to 3 hours; 3 to 4 hours; 4 hours or more. The assessment of TV viewing using parental report has been shown to correlate moderately ( $r=0.60$ ) with 10 days of TV diaries among young children.

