## **Background**

### The Problem to Address: Obesity and Physical Inactivity in Preschool Children

The Gulf States of Louisiana, Mississippi, and Alabama each rank in the top ten for highest prevalence of childhood obesity, adult obesity, physical inactivity, type 2 diabetes, and hypertension. In Louisiana, obesity affects 13.8% of children aged 3 to 5 years and 29% of all children aged 2 to 17 years, which is substantially higher than the national prevalence. Obesity during childhood contributes to several serious comorbidities including diabetes, hypertension, ischemic heart disease, stroke, asthma, and polycystic ovary syndrome. Moreover, children with obesity are at higher risk for premature mortality.

Increased physical activity and decreased sedentary behavior are key recommendations to reduce the risk for obesity and related comorbidities. Low levels of physical activity and high levels of sedentary activity contribute to a variety of mental and physical health consequences during the preschool and early childhood years, including obesity, high blood pressure, behavioral problems, academic problems, irregular sleep, and feelings of sadness and boredom. Indeed, physical activity and screen-time together explain 65% of the variance in children's body mass index (BMI) from age 3 to 7 years. However, children are not obtaining sufficient levels of physical activity and are spending too much time in sedentary pursuits. Nearly half of preschool-aged children do not meet the recommended 1 hour of moderate-to-vigorous physical activity (MVPA) each day. Screens are highly prevalent in children's lives due to increased device availability and marketing efforts, and preschool children are estimated to spend between 1.5 and 7.0 hours each day in screen-time despite recommendations for 2 or fewer hours of daily screen-time.

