### **Primary Endpoints and Data Analysis Plan**

Primary endpoints will include 1) changes in objective child physical activity, as measured via 7-day accelerometer at baseline and 1 year, including minutes/day MVPA in childcare center, minutes/day MVPA total; 2) classroom observation of child screen-time, as measured with EPAO observation method to quantify average minutes/day screen-time in childcare center; and 3) parent reports of child screen time to quantify minutes/day screen-time total. Age, sex, BMI z-score, and sociodemographic characteristics will be included as covariates. We will also assess the cross-sectional and longitudinal associations among sedentary behavior (by screen-time observation/self-report and by accelerometry), physical activity (by accelerometry), and fundamental motor skills.

A repeated measures ANCOVA model will be used to test for effects of policy implementation on each dependent continuous variable (minutes/day MVPA in childcare center, minutes/day screen-time in childcare center, minutes/day MVPA total, minutes/day screen-time total). Covariates will include age, sex, BMI z-score, and sociodemographic characteristics. Correlations and a repeated measures ANCOVA will be used to test for the relationships among sedentary behavior, physical activity, and change in fundamental motor skills.

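### The parent screen-time survey, as described, names four devices and gives tablet use no stated place, so the change in the primary total screen-time endpoint could be biased in either direction if device mix shifts over the year

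*Combined protocol and SAP*

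**What the plan says.** The Screen time paragraph of the Procedures section splits measurement by setting. Classroom observation covers the center, and the plan uses "parent-report for screen-time outside of the childcare center". The parent survey is adapted from a published questionnaire and collects time "separately for TV, computer, games console and smartphone". "For each item the parent will be asked to report the time the child spent using it for" a typical weekday and a typical weekend day, with answers in bands from none to an open top category of four hours or more.

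The Primary Endpoints and Data Analysis Plan lists among the primary endpoints "parent reports of child screen time to quantify minutes/day screen-time total". On the analysis it says: "A repeated measures ANCOVA model will be used to test for effects of policy implementation on each dependent continuous variable". No comparison group is described. On the interval, the Number of Subjects and Subject Timeline section says: "Each child will participate in the study for approximately 1 year".

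In the Background, the plan attributes the prevalence of screens in children's lives partly to "increased device availability and marketing efforts".

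**The concern.** The endpoint is called a total, but the items described are four named devices. Tablets are not mentioned anywhere in the documents. Nor is there a catch-all item, a single overall screen-time question, or an instruction assigning tablet use to one of the four items. A parent whose child uses a tablet may leave that time out, or may enter it under computer or smartphone, and may answer differently a year later.

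What is at stake is the change between visits, because that is what the plan credits to the policy. If viewing moves between a listed device and one that goes unrecorded, the measured total moves although behavior has not. With one group measured twice, nothing in the design would reveal this. The planned covariates (age, sex, BMI z-score and sociodemographic characteristics) do not measure device use.

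**Working it through.** **1. Coverage.** The item list in Procedures has four devices. The endpoint in the Primary Endpoints and Data Analysis Plan is total daily screen-time. Nothing in the documents links tablets to either. This step needs no arithmetic.

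**2. Level versus change.** Let T be true screen-time outside the center and u the tablet time that reaches no item. The measured value is M = T − u at each visit, so

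change in M = change in T − change in u.

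- If u is the same at both visits, the level is too low by u and the change is unbiased.
- If u rises, the measured total shows a fall that is false or too large.
- If u falls, a true fall is hidden or shrunk.

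**3. Illustrative size of the unmeasured level.** Inputs from the Specific Aims section: 4.1 h/day of screen-time on average, and 1.3 h/day in childcare centers. They come from different cited sources, so subtracting one from the other is an assumption. The tablet shares are also assumed.

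- Overall: 4.1 × 60 = 246 min/day. In center: 1.3 × 60 = 78 min/day.
- Outside the center: 246 − 78 = 168 min/day.
- Shares of 10, 20 and 30%: 16.8, 33.6 and 50.4, or about 17, 34 and 50 min/day.
- If the in-center time is counted on 5 of 7 days: 78 × 5/7 = 55.7, and 246 − 55.7 = 190.3. The same shares give about 19, 38 and 57 min/day.

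These are upper values for each share, because tablet time entered under another item is still in the total. On the 168-minute base, an unrecorded 10% shift would look like a change of up to about 17 min/day.

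**4. Could a smaller shift produce a significant result?** The Power Analysis gives 266 children, 25% dropout and a significance level of 0.05. It gives no figure for screen-time. 266 × 0.75 = 199.5, so take 199 completers. Suppose true screen-time does not change, but 10 to 30% of children move 30 to 60 min/day to an unrecorded device (assumed). The mean false fall runs from 0.10 × 30 = 3 to 0.30 × 60 = 18 min/day. For a two-sided paired normal test, ignoring covariates and clustering by center, SE = SD/√199 and

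P(reject) = Φ(fall/SE − 1.96) + Φ(−fall/SE − 1.96).

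| Assumed SD of change (min/day) | 3 min fall | 18 min fall |
|---|---|---|
| 60 | 11% | 99% |
| 90 | 8% | 81% |
| 120 | 6% | 56% |

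The nominal rate is 5%. The switching rates and SDs are not in the documents. The table shows only that modest shifts could matter at this sample size.

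**The case against.** The strongest reply is that the Procedures text is a one-line summary of an adapted form whose wording is not reproduced. The form may mention tablets, or parents may naturally enter them under computer or smartphone. A reader might infer that the survey is shown to exclude tablets and that the endpoint will therefore show a false fall. The documents do not support that. They establish only that the protocol names no tablet item and does not say where tablet time is counted.

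Three further points stand. First, unmeasured minutes are not bias in the change: stable tablet use cancels. Second, nothing in the documents gives a rate of switching to tablets during the study. The Background remark on device availability explains why screens are common; it does not predict a shift between visits. Third, answers are banded, with an open top category, and the conversion to minutes is not stated, so a given shift in viewing need not appear minute for minute.

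It would also be tempting to apply the tablet shares to the full 246 min/day, which gives about 25, 49 and 74. That base is wrong, because the parent report covers only time outside the center.

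It is fair, too, that any time trend threatens a one-group before/after design and that tablets are one example. But this example can be closed by a survey item, which most time trends cannot.

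**Conclusion.** The point holds as a measurement gap with a conditional consequence. As described, the survey gives tablet time no defined place, and a primary endpoint called a total rests on it. The level may be understated. The before/after change is biased only if unrecorded tablet time differs between visits, and the bias may go either way.

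The size cannot be computed from the documents. On the plan's own averages and assumed tablet shares of 10 to 30%, the unmeasured level is at most about 17 to 50 min/day, and an unrecorded 10% shift would look like a change of up to about 17 min/day. This rests on subtracting two averages from different sources and on none of the tablet time being entered elsewhere.

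The observed in-center screen-time endpoint and both MVPA endpoints do not use this device list and are unaffected. This is a cheap improvement to one primary endpoint, not a flaw that undermines the study.

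**What to change.** Before baseline, add a tablet item to the parent survey, for a weekday and a weekend day with the same response bands. Alternatively, reword the last item so that it covers smartphone or tablet. Use identical wording at both visits, and state in the analysis plan that this time is included in total daily screen-time. If the form already covers tablets, it is enough to say under which item.

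The change must not be made at follow-up only, because a new item counted at one visit would create an artificial rise.

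The cost is two extra response lines and a small further departure from a source questionnaire that is already adapted. The sample size does not change.

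### The parent screen-time options overlap at exactly 1, 2, 3 and 4 hours and are open above 4 hours, yet they feed a continuous minutes/day primary endpoint: modest noise, and falls within the top option recorded as zero

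*Combined protocol and SAP*

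**What the plan says.** The Screen time paragraph of Procedures assigns screen time outside the center to a parent survey adapted from a published instrument. The questions are asked "separately for TV, computer, games console and smartphone) on weekdays and weekend days", once for each of "a) a normal weekday and (b) a normal weekend day". That makes 4 devices × 2 day types = 8 banded answers per child per wave. The options are "with response options: none; 1 to 30 minutes; 31 minutes to 1 hour; 1 to 2 hours; 2 to 3 hours; 3 to 4 hours;" and, at the upper end, "2 to 3 hours; 3 to 4 hours; 4 hours or more".

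The Primary Endpoints and Data Analysis Plan lists "parent reports of child screen time to quantify minutes/day screen-time total" as a primary endpoint. For the analysis: "A repeated measures ANCOVA model will be used to test for effects of policy implementation on each dependent continuous variable". Total screen-time minutes/day is one of the variables named there.

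The documents do not say:
- how a band becomes a number of minutes;
- what value the open top option takes;
- which option an exact hour belongs to;
- how the eight answers combine into one daily figure.

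**The concern.** The 30-minute boundary is exclusive, because one option stops at 30 minutes and the next starts at 31. The boundaries at 1, 2, 3 and 4 hours are not. A parent who means 2 hours at both visits can properly tick either of two options each time, and the analysis would read a switch as change.

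The open top option raises a different problem. A child whose use of one device falls substantially but stays above 4 hours is ticked the same way at both waves, so the fall disappears. A switch at a boundary is noise, and a larger sample reduces its effect. A fall lost in the top option is an error in one direction, towards no effect, and a larger sample does not remove it. The aim is to detect a fall in screen time after the regulations, so both errors reach a primary comparison.

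**Working it through.** The plan gives no scoring figure to reproduce, so the check takes the printed bands and varies what is unstated.

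**Inputs from the documents.** Bands in minutes: 0; 1–30; 31–60; 60–120; 120–180; 180–240; 240 and above. Enrollment is 266 with 25% dropout (Power Analysis), so 266 × 0.75 = 199.5, or 199 completers.

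**Assumed inputs.** Each band is scored at its midpoint, lower limit or upper limit. The top option is scored at 240, 270, 300 or 360 min. Weekday and weekend answers are weighted 5/7 and 2/7.

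**Step 1. False change on one device for an unchanged answer, with the same switch on both day types.** Jump = score of upper band − score of lower band.

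| Boundary | Midpoint | Lower limit | Upper limit |
|---|---|---|---|
| 1 h | 90 − 45.5 = 44.5 | 60 − 31 = 29 | 120 − 60 = 60 |
| 2 h | 150 − 90 = 60 | 120 − 60 = 60 | 180 − 120 = 60 |
| 3 h | 210 − 150 = 60 | 180 − 120 = 60 | 240 − 180 = 60 |
| 4 h, top = 240 | 30 | 60 | 0 |
| 4 h, top = 270 | 60 | 90 | 30 |
| 4 h, top = 300 | 90 | 120 | 60 |
| 4 h, top = 360 | 150 | 180 | 120 |

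The jump of about 45 to 60 min therefore holds at 1 to 3 h under midpoint scoring. At 1 h the range over scorings is 29 to 60 min, and at 4 h it is 0 to 180 min.

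**Step 2. Only one day type switches (midpoints, 1 to 3 h).**
- Weekday only: 44.5 × 5/7 = 31.8 to 60 × 5/7 = 42.9 min/day.
- Weekend only: 44.5 × 2/7 = 12.7 to 60 × 2/7 = 17.1 min/day.

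**Step 3. Effect on the mean change.** Suppose a parent at a boundary picks either band with probability 1/2, independently at each wave. The change is +J or −J with probability 1/4 each and 0 otherwise. Its mean is 0 and its SD is J × √0.5: 31.5 min for J = 44.5 and 42.4 min for J = 60.

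If a share q of 199 completers sits at a boundary on one device, the added component of the standard error is J × √(0.5q/199).
- q = 0.1: 0.71 to 0.95 min.
- q = 0.3: 1.22 to 1.65 min.
- q = 1: 2.23 to 3.01 min.

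This component combines in quadrature with the rest of the standard error, so the net increase is smaller than these figures.

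**Step 4. How much is overlap and how much is band width?** With exclusive bands 61–120, 121–180 and 181–240, the midpoints are 90.5, 150.5 and 210.5. The steps from 45.5 upward are then 45, 60 and 60 min. A one-minute real difference across a boundary still scores 45 to 60 min, so removing the overlap ends the ambiguity but not the step.

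**Step 5. The open top.** A fall from 6 h to 4.5 h on one device is 90 min. Both values lie in the top option, so the recorded change is 0 under every scoring. With the top split at 5 and 6 h, the two values fall in 300–360 (midpoint 330) and 240–300 (midpoint 270), and the recorded fall is 60 min.

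**The case against.** The case for leaving the item alone has real force.

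- **Size.** A reader might take 45 to 60 minutes as a fixed error. The documents do not support that, because they give no scoring rule. The figure needs midpoints and the same switch on both day types.
- **Bias.** A reader might infer that the overlap biases the policy effect. It does so only if boundary choices differ systematically between waves, and nothing in the documents suggests this. If parents tend to tick the same way twice, even the noise in Step 3 is smaller.
- **Ceiling.** The Background section says "preschool children are estimated to spend between 1.5 and 7.0 hours each day in screen-time", and a reader might conclude that many children reach the top option. That range is total daily screen time, whereas the limit applies to one device on one day type. Spread evenly over four devices, 7.0 h is 1.75 h each. The parent report also covers only time outside the center, and eligible children spend at least 6 hours a day there on 5 days a week.
- **The 2-hour recommendation.** It lies on a shared boundary, so a reader might infer that children would be misclassified against it. No endpoint classifies children that way. The recommendation concerns total screen time rather than one device, and screen time in the center is measured by observation.
- **Form not available.** The questionnaire itself is not in the documents, and its printed options may differ from the protocol's description.

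The first four points stand and limit the size of the concern. The last is a reason to check the form. None of them removes the overlap or the open top from the plan as written, or supplies the missing scoring rule.

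**Conclusion.** The point holds in a limited form. Two facts need no assumption: four boundaries are shared, and a fall contained in the top option on one device and day type is recorded as zero.

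The overlap costs precision, and the cost is modest: a standard-error component of about 1.2 to 1.7 min, assuming 199 completers, 30% of children at a boundary on one device, independent 50/50 choices and midpoint scoring. Much of the individual step comes from band width.

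The open top matters more in kind, because it pulls a true reduction towards zero. Its frequency, and so its effect on the mean, cannot be derived from the documents. The 0 to 180 min spread at 4 h shows how far the result at that boundary depends on an unwritten scoring choice. This is worth correcting because the correction is cheap. It does not threaten the study.

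**What to change.** In the Screen time paragraph of Procedures, and on the survey form:

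1. Make the options exclusive above 1 hour: more than 1 and up to 2 hours, more than 2 and up to 3, more than 3 and up to 4.
2. Replace the open option with further bands, for example more than 4 and up to 5, more than 5 and up to 6, and more than 6 hours.
3. Use the identical form at baseline and at 1 year.

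In the Primary Endpoints and Data Analysis Plan, state a fixed minute value for each band and how the device and day-type answers combine into minutes/day. Add a sensitivity analysis over the value given to the top band.

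The cost is a short survey edit and a few sentences of analysis text. The downside is slightly less comparability with the source survey, which the plan already adapts. If baseline forms have already been completed with the current options, keep them at follow-up so that the waves match, and add only the scoring rule and sensitivity analysis.

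Entry in hours and minutes, or an interval-censored analysis, would deal with band width more fully. Both are optional: the documents do not show that parents recall minutes more accurately than bands, and an interval-censored model for a sum of eight banded answers is a larger change to the analysis.
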